1.2 Name and Description of Investigational Product or Intervention

The communication skills training (CST) program for clinicians will encourage the use of best practices in conducting family meetings where teams give bad news and elicit goals of care as well as build team collaboration. The CST will be developed by modifying the VitalTalk³⁶ CST to adapt it to interprofessional training, the pediatric CICU setting, and CHOP-developed Family Meeting Resources. The family-facing intervention includes standardized preparation for family meetings and provides a written summary of the family meeting to families. The combined aspects of the intervention are now known as CICU Teams and Loved ones Communicating (CICU TALC).

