2.2 Secondary Objectives (or Aim)

The secondary objectives are to:

- Evaluate CICU clinicians' perceived feasibility and acceptability with the CST
- Evaluate CST impact on communication skills and team function in the actual family meeting
- Evaluate clinicians' burnout rates and changes that CICU clinicians have implemented regarding family meetings due to the 2020 COVID-19 pandemic
- Evaluate the fidelity of clinician behavior to the intended intervention
- Learn about parents perspectives about communication challenge
- Learn about parental acceptability about parent-facing intervention elements including preparation for family meetings in the CICU and the written summary received after the family meeting

The following secondary endpoints will be used to assess CICU clinicians' perceived feasibility and acceptability with CST:

- Perceived acceptability of CST
- Metrics of enrollment rates and missing data
- Post-CST clinician survey
- Acceptability interview carried out with randomized subset of 8 intervention participants.

The following secondary endpoints will be used to assess CST impact on clinician behavior in simulated family meetings:

- Communication skill acquisition
- Team collaboration

The following secondary endpoints will be used to assess CICU clinicians' burnout rate and changes that CICU clinicians have implemented regarding family meetings due to the 2020 COVID-19 pandemic:

- Maslach burnout score¹⁰³
- COVID change in practice survey

The following secondary endpoints will be used to assess CST impact on clinician behavior in actual family meetings:

- Communication skill acquisition
- Team collaboration
- Team member perception and satisfaction with collaboration
- Fidelity of clinician behavior to intervention

The following secondary endpoints will be used to assess parents' perspectives about communication challenges in the CICU:

- Satisfaction feelings when communicating with the clinical team with decision-making
- Understanding of patient's medical condition
- Trust in medical team
- Levels of anxiety, depression, and post-traumatic stress

The following secondary endpoints will be used to assess parents' acceptability of the parent-facing elements of the intervention; including preparing for the meeting and their perception of the written summary after the family meeting

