3 INVESTIGATIONAL PLAN

3.1 General Schema of Study Design

This is a non-randomized cohort study with pre and post assessments around an intervention.

Clinicians and Parents Participating in Co-design of Intervention

Eligible clinicians will be approached in person and via email. If they express willingness to participate in the co-design portion of the study, they will be consented. Eligible parents of children previously hospitalized in an ICU will be approached via email or phone. If they express willingness to participate in the co-design process, they will be consented. After enrollment into the study, clinicians and parents will participate in a total of 11 sessions as focus groups to gather feedback on the CST program. Participants will be asked which aspects of the training they believe would facilitate their participation in a family meeting and sense of collaboration, which opportunities might have been missed and whether the training addressed the core competencies in collaboration. After the 11 sessions have been completed, participants will then be asked to complete a survey measuring their engagement

in the co-design process. Based on participant experience and feedback in the co-design sessions, the training will be modified to ensure its goals are met.

Clinicians Participating in Intervention

Clinicians in the CICU eligible for the intervention will be approached via email and in administrative meetings and individually consented at the beginning of the study.

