- *Parental feelings about communication with the clinical team:* myICU¹¹⁹ is an 11 item tool adapted by the authors of the tool to assess a surrogate’s perceptions of how comfortable the surrogate feels discussing potential concerns they have with their child’s medical team regarding their child’s care in the ICU.
- *Parental involvement in other family meetings*
- *Fidelity of Parent Preparation and Acceptability:* Parents will be surveyed on whether they were given the Family Preparation Worksheet and whether clinicians followed up on how they used the worksheet. They will be asked what they thought of the worksheet. They will also be asked about their acceptability of the Family Meeting Summary Worksheet. The use and acceptability survey was adapted from a Shared Decision Making tool.¹²⁰ See Appendix 11.15 for specific items.
- *Medical record review:* Patient data will be retrieved from Epic and PC⁴ national database registry. Data listed below are main patient record variables. See Appendix 11.18 for full list of PC⁴ variables
 - Child’s name
 - Child’s MRN#

- Child's date of birth
- Child race/ethnicity
- Parent/legal guardian race
- Parent/legal guardian contact number
- Parent/legal guardian e-mail address
- Parent/legal guardian address
- Length of stay in the CICU
- Length of stay in the hospital
- EPIC Problem List
- Medication list and administration dates throughout hospitalization
- Limitations of interventions during study period
- Date of limitations of interventions during study period
- ICD-9 codes associated with hospitalization
- Date of discharge from CICU / Date of death/ discharge from hospital
- Discharge disposition from CICU and hospital (floor / home / rehab facility / palliative care / hospice)
- Palliative care consult
- Ethics consult
- Gestational age
- Fundamental Cardiac Diagnosis
- Chromosomal abnormalities
- Syndromes
- Cardiothoracic surgery and date
- Primary insurance type
- Discharge 30 day mortality status
- Number of prior cardiothoracic operations
- Reason for CICU encounter
- Non-cardiothoracic surgery
- Encounter cardiothoracic diagnosis
- Encounter medical diagnosis
- DNR/DNI on file
- Withdrawal of life sustaining therapy
- Bleeding requiring reoperation and date
- Unplanned reoperation/reintervention and date
- Sternum left open and date
- Cardiac arrest and date
- Stroke and date
- Risk group as measured by the STAT mortality category
- operative or post-operative complications

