Team function will be analyzed for simulated family meetings by comparing the change in the number of minutes that clinicians from each discipline speak in pre and post-CST meetings using linear regression and controlling for the length of the meetings.

To assess the impact of the CST program in actual family meetings, audio recordings from actual family meetings will be coded and compared to coded audio recordings from pre-intervention actual family meetings. Since there are generally at least 2 clinicians in each team encounter, we will examine the individual skill acquisition within each part of the team encounter. Within each discipline, there are several clinicians involved in multiple team meetings. We will use fixed-effects regression with a clinician identifier variable as a covariate so that we can examine the effect of CST intervention on skill acquisition, adjusting for the effects of individual clinicians.

Team function will be analyzed in the same way as in simulated meetings by comparing the change in the number of minutes that clinicians from each discipline speak in pre and post-CST meetings using linear regression and controlling for the length of the meetings.

The difference in team member perception and satisfaction with collaboration will be measured after their participation in clinical encounters both pre and post-CST by administering the modified Baggs CSACD-N tool to all clinician team members who participate in an actual encounter. This tool will capture each discipline's experience with collaboration with other team members and satisfaction with care decisions. Means and standard deviations will be calculated for the tool and t-tests will determine if there are significant differences for each discipline pre and post-CST.

Hypotheses will be tested using logistic regression modeling with significance of the two-tailed hypothesis tests set at alpha equal to 0.05.

Clinician perception of the usefulness of CST and satisfaction with the training will be identified by descriptive statistics and differences in the mean and median scores will be calculated to determine retention in perceptions of usefulness one month after the training.

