## Statistical Analysis Plan

Aim 2: Pilot test the co-design-adapted CICU TALC with CICU parents and clinicians to determine:

a) Acceptability of intervention: Hypothesis: Respondents will endorse above a critical threshold of acceptability on satisfaction instruments to 20 clinicians and 23 parents and in semi-structured interviews.

Analytic plan: A constructivist grounded theory approach will guide qualitative analysis of interview transcripts regarding acceptability of the intervention. Descriptive statistics will be calculated for quantitative data from the acceptability survey.

b) Feasibility of enrollment and data collection, and fidelity: Hypothesis: Feasibility will be defined by: i) 30% parental and 50% clinician enrollment and consent rates, and 80% subject retention, and attrition; ii) ability to collect outcomes data from 46 patients (CICU length of stay), from 46 parents and from 50% of eligible team members. and iii) intervention fidelity with 95% of enrolled parents and clinicians receiving parent-directed and team-directed interventions.

Analytic Plan: Data completeness and accuracy will be monitored. I will calculate descriptive summaries including means and standard deviations for continuous variables, and proportions for categorical variables. As appropriate for pilot trials, analyses will focus on estimating proportions of binary feasibility and fidelity endpoints and constructing 95% CIs. Analyses of parent-reported outcomes will primarily be descriptive. Means and standard deviations along with 95% confidence intervals will be calculated.

c) Impact of CICU TALC on CICU parent and team behavior in family meetings. Hypothesis: the intervention will increase parent speaking time by 60%, elicitation of parental concerns to 40%, and response to parental emotion by 30%. I will audio record 230 CICU family meetings occurring before CICU TALC is initiated and 230 after initiation and use quantitative methods to measure pre-vs-post differences in a) speaking time of parents and physicians; b) elicitation of parental concerns; and c) response to parental emotion.

Analytic Plan:

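### The pre/post change in actual family meetings is credited to CST, but the post phase brings in CST and family preparation together, so it can only speak to the CICU TALC package

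*Protocol*

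**What the plan says.** Protocol 3.1 gives the design: "This is a non-randomized cohort study with pre and post assessments around an intervention". The secondary objective in 2.2 reads "Evaluate CST impact on communication skills and team function in the actual family meeting". Section 6.3.2 gives the method: "To assess the impact of the CST program in actual family meetings, audio recordings from actual family meetings will be coded and compared" with recordings from the pre-intervention phase. A regression with a clinician identifier is then fitted so that "we can examine the effect of CST intervention on skill acquisition", with adjustment for the individual clinician. Section 6.4 repeats this for actual encounters. Team function (minutes spoken by clinicians of each discipline) is compared between phases, controlling for meeting length.

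Section 1.2 describes two parts. The training is for clinicians. Separately, "The family-facing intervention includes standardized preparation for family meetings", with a written summary afterwards. The combination is named CICU TALC. Sections 3.1, 3.1.5 and 4.5.6 mention the family worksheet for post-phase dyads only, and its use is left to the family. Under 5.1.1, parents are asked whether they were given it and "whether clinicians followed up on how they used the worksheet".

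The SAP uses the package name. Aim 2c concerns the impact of CICU TALC on parent and team behaviour and hypothesises that "the intervention will increase parent speaking time by 60%, elicitation of parental concerns to 40" per cent, with a further target for response to parental emotion.

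**The concern.** A before/after contrast estimates the effect of everything that changes at the phase boundary. Here the training and the family preparation both start there, yet the protocol names only the training as the cause of any change in clinician skill or team function. The two documents would also label overlapping results differently. Response to emotion sits within SPIKES in protocol 6.2, under the heading of CST impact, and is also a SAP Aim 2c outcome under CICU TALC.

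What is at stake is the conclusion. Section 2 gives the study's purpose as assessing whether the training changes clinician behaviour. If the protocol wording is followed, part of a change produced by better-prepared families could be published as a training effect. The stepped wedge study foreshadowed in 6.4 could then inherit a component-specific claim that this design cannot support.

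**Working it through.** **1. What each phase contains**

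| Element | Pre phase | Post phase | Where |
|---|---|---|---|
| Clinician CST | No | Yes | Protocol 3.1.3 to 3.1.5 |
| Family preparation worksheet | Not mentioned | Available, use optional | Protocol 3.1, 3.1.5, 4.5.6 |
| Survey section on the worksheet | None listed | Section 1 | Contents list, Appendices 11.14 and 11.15 |
| Written summary | Not mentioned | After the meeting | Protocol 1.2, 4.5.6 |

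The pre-phase entry for the worksheet is an inference from silence; no sentence excludes it. The summary follows the meeting, so only the preparation can affect the recorded conversation it belongs to. The clinicians' own pre-meeting worksheet in 3.1.2 is a different form.

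**2. What the contrast identifies**

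Let C be the change due to training, W the change due to family preparation, and I any interaction. Leaving other calendar changes aside,

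post − pre = C + W + I.

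Only the sum can be estimated. The clinician identifier removes stable differences between clinicians and leaves C + W + I untouched; so does adjustment for meeting length. The SAP's adjusted models name gender and years of experience first, then other characteristics if sample size allows; worksheet use is not named. Optional use gives some variation, but only within the post phase and by the families' own choice, so a worksheet term would not cleanly isolate C either.

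**3. How W could reach a clinician outcome**

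The codes in 6.2 score what clinicians say, so the route is indirect. A prepared parent may raise more concerns or show more emotion, which gives clinicians more openings. Section 5.2.1 treats a larger total of empathic expressions as a change in clinician behaviour and does not divide by openings. The total can then rise while the response rate per opening stays the same.

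**4. Scale, by illustration only**

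No figure in the plan tests this point. The 20 clinicians and the 3 pairs in 6.4 rest on inputs held in cited sources. The baselines and worksheet effects below are assumptions; meetings are taken as independent and phases as equal. Meeting numbers come from protocol 6.4 (20), 3.1.5 (23 and 28) and the SAP (230).

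Chance of a significant rise = Φ[(Δ − 1.96·SE0)/SE1], where SE0 = √(2p̄(1−p̄)/n) and SE1 = √([p0(1−p0) + p1(1−p1)]/n).

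Example with C = 0, p0 = 0.20, p1 = 0.30:
- n = 230: SE0 = 0.0404, SE1 = 0.0401; (0.10 − 0.0791)/0.0401 = 0.52; Φ = 0.70.
- n = 23: SE0 = 0.1277, SE1 = 0.1268; (0.10 − 0.2503)/0.1268 = −1.18; Φ = 0.12.

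Over baselines of 20% to 40%:

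| Meetings per phase | Worksheet adds 10 points | Worksheet adds 20 points |
|---|---|---|
| 20 | 9–11% | 24–28% |
| 23 | 10–12% | 27–31% |
| 28 | 11–14% | 32–37% |
| 230 | 58–70% | 99% or more |

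For the indirect route, suppose openings rise 60% (the SAP's speaking-time figure, borrowed as an assumption) and the response rate per opening is constant. The share of meetings with at least one empathic response is 1 − exp(−λ), where λ is the expected number of responses per meeting.
- λ from 0.5 to 0.8: 39% to 55%.
- λ from 1.0 to 1.6: 63% to 80%.

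These rises would be significant in 18% and 23% of studies at 23 meetings per phase, and in 92% and 98% at 230.

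**The case against.** The best defence is that CST is not always the training alone. The abstract's fifth objective refers to parent-facing aspects of the CST program, and its intervention paragraph lists parent preparation among the aspects of the intervention. On that reading 6.3.2 already means the package. This stands in part: the terminology is loose, and no sentence says that the design isolates one component. But 3.1 and 3.1.4 use CST for a 10-hour clinician course, and 1.2 gives the combination its own name. A reader of 2.2 and 6.3.2 will take CST as the training.

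It is also fair that this is a non-randomised pilot whose primary endpoint (6.1) is qualitative. That limits the weight of the point.

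Some stronger readings are tempting, and the documents do not support them:
- *Parents' talk would be scored as clinician skill.* SPIKES and NURSE score clinicians' own acts.
- *A rise in elicitation of concerns or parent speaking time would be reported as a CST effect.* Both are named only in the SAP, which already credits CICU TALC.
- *The sizing hypothesis in 6.4 is affected.* It concerns simulated meetings, for which no family worksheet is described; only the later text on actual encounters repeats the problem.
- *Worksheet follow-up alone would reach the SAP's 40% for elicitation.* One can pick inputs that do so: an assumed 25% baseline with follow-up coded as elicitation in an assumed 20% of meetings gives 0.25 + 0.75 × 0.20 = 0.40. Both inputs are invented. The sum ignores the proficiency cutoffs the SAP applies, and the coding manual is not in the text supplied. Section 5.1.1 does not say that follow-up happens within the recorded meeting.
- *The worksheet confounds the SAP analysis.* For the package, preparation is part of the treatment.

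**Conclusion.** The point holds as one of attribution. In actual meetings the pre/post contrast can at most support a claim about CST plus family preparation, and the CST-only wording in protocol 2.2, 6.2, 6.3.2 and the actual-meeting text of 6.4 should not stand. SAP Aim 2c already has the right label.

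This rests on the inference that pre-phase families did not have the worksheet. Its numerical size is unknown: the documents give no baseline and no worksheet effect, and use is optional. The illustration shows that a modest worksheet effect would seldom give a significant result at 20 to 28 meetings per phase but often would at 230. At 230 it would be a misattribution only if the result were reported under the protocol's label. No sample size changes. It is worth correcting because it alters what the study may conclude at almost no cost.

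**What to change.** **Main change.** In protocol 2.2, 6.2, 6.3.2 and the actual-meeting text of 6.4, name the estimand as the effect of CICU TALC (CST plus parent preparation), as the SAP does. Add a sentence that the change in actual meetings will not be attributed to CST alone. State whether any pre-phase family had the preparation worksheet. The cost is a wording amendment and a less specific claim.

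**Optional.** Both items are best settled before recordings are scored.
- Give clinician follow-up of the family worksheet its own code and report elicitation with and without it. Keep it in the main score: it may be behaviour the training was meant to produce, and removing it could bias the result downward. The cost is one code and one extra line of results.
- Describe post-phase results by worksheet use, from the REDCap and Visit 3 data already planned, labelled exploratory. Use is self-selected and only about 30 evaluable post-phase dyads are expected, so this cannot isolate CST.

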Clinician team members participating in an observed family meeting who will not undergo the CST (because they were not eligible, did not wish to participate in the study, or were not approached because sufficient clinicians were already enrolled) will be consented before the scheduled meeting to being audio or video recorded only in the observed family meeting. They will also be administered a survey at the end of the meeting. Clinicians not participating in the intervention will be enrolled for only the duration of their observed family meeting and may be enrolled more than one time during the course of the study.

Parent-patient Dyads Participating in the Survey or Interview Prior to Intervention

Potential subjects will be screened using the protocol inclusion and exclusion criteria. Parent-patient dyads will be recruited into the study in person or over the phone. The goal for enrollment will be 100 parent-patient dyads for the survey and up to 30 parent-patient dyads for the interview. 100 parent-patient dyads who are enrolled will be given an online survey on a laptop computer or via email to obtain baseline data assessing parental satisfaction, understanding, trust in the clinical team and emotional well-being. Medical record review of this group of patients will utilize EPIC and the PC⁴ database, but will not require patient or parent involvement. 30 enrolled parent-patient dyads will participate in an interview assessing their experiences in family meetings and their perspectives on communication with the clinical team.

Parent-patient Dyads Participating in the Survey or Interview After Intervention

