3.1.5 Follow-Up Phase

Clinicians Participating in Intervention: After CST, a set of actual family meeting encounters with these trained clinicians will be audio recorded and coded, ensuring there are 23 meetings with each category of person trained. We estimate a total of 28 meetings will need to be recorded in order to obtain 23 meetings with each discipline. Clinicians participating in the intervention will complete an online survey after the actual family meeting that they are observed participating in.

This survey will measure team member perception and satisfaction with collaboration. We will administer the modified Baggs CSACD-N tool to all clinician team members who participate in an actual encounter, which will capture each discipline's experience with collaboration with other team members and satisfaction with care decisions.

Clinicians Not Participating in Intervention: Consented non-participating clinicians will have their normal, scheduled family meetings. Actual family meeting encounters with these clinicians will be audio or video recorded and coded. Clinicians not participating in the intervention will complete the same online survey as those clinicians participating in the intervention after the observed actual family meeting.

Parent-patient Dyads Participating in the Survey or Interview After Intervention: Potential subjects will be screened using the protocol inclusion and exclusion criteria. Parent-patient dyads will be recruited into the study in person, over the phone, or via e-mail. The goal for enrollment will be up to 50 parent-patient dyads, with 30 evaluable parent-

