4.5.1 Clinicians Participating in Intervention: Visit 5-30

- Clinician audio recorded during actual family meeting
- Administration of follow-up online survey about clinicians' perception of team function in person or via email

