The following secondary endpoints will be used to assess clinician burnout and changes in communication in family meetings during COVID-19 pandemic

- The Maslach burnout scale, which uses Likert-type scales to measure aspects of burnout syndrome, including emotional exhaustion, depersonalization, and decreases in feelings of accomplishment.^{103,127}
- COVID-19 impact on communication in family meetings is a novel tool with 18 questions measuring the modality of communication with families and colleagues prior to during COVID-19 pandemic.

The following secondary endpoints will be used to assess CST impact on clinician behavior only in actual family meetings:

- *Modified Baggs CSACD-N tool*^{94,128}: The Baggs CSACD-N tool will measure team member perception and satisfaction with collaboration both pre and post-CST and will be given to all participating clinician team members. This tool will capture each discipline's experience with collaboration with other team members and satisfaction with care decisions. The difference in team member perception of collaboration will be measured using the CSACD-N pre and post-CST training. Means and standard deviations will be calculated for the tool and t-tests will determine if there are significant differences for each discipline pre and post-CST.
- Qualitative thematic analysis of family meetings that will identify if there are differences in themes prior to and after CST

The fidelity of the intervention implementation will be assessed by a Fidelity Checklist.

- The fidelity checklist will be scored by a study team member while reviewing the family meeting recording and reviewing information in Epic and parental survey responses. A summary score will be calculated for each family meeting conducted and descriptive statistics will be calculated for the post-intervention family meetings.

The following secondary endpoints will be used to assess parents' perspectives about communication challenges in the CICU when talking with the clinical team:

- In-person interviews prior to the intervention: These interviews will assess parents' experiences in communicating in the CICU with the clinical team. A constructivist grounded theory approach will guide qualitative analysis of interview transcripts.

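### The CSACD-N collaboration scores are compared by per-discipline t-tests with no clinician term, although the same clinician can complete the survey several times, so the 5% level is not in general held

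*Protocol*

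**What the plan says.** Protocol 6.3.2 describes "administering the modified Baggs CSACD-N tool to all clinician team members who participate in an actual encounter", before and after training. The analysis is means, standard deviations and then this: "t-tests will determine if there are significant differences for each discipline pre and post-CST". Section 6.2 gives the same test, introduced by "The difference in team member perception of collaboration will be measured using the CSACD-N pre and post-CST training". Neither section says whether the t-test is paired or unpaired, and neither includes a clinician or meeting term.

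The protocol expects clinicians to recur:
- Section 6.3.2: "Within each discipline, there are several clinicians involved in multiple team meetings".
- Section 3.1, on clinicians outside the intervention: they "may be enrolled more than one time during the course of the study".
- The section headed "Clinicians Participating in Intervention: Visit 5-30" attaches a recorded meeting and a survey to those visits. Section 4.5.3 does the same for visits 2-17 of non-participating clinicians.

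Because of this recurrence, section 6.3.2 puts a clinician identifier into the regression for skill acquisition. It does not do so for CSACD-N. The SAP's outcomes are speaking time, elicitation of parental concerns and response to emotion. Its mixed model is conditional on sample size and on significant univariate results, and CSACD-N is not among its outcomes.

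**The concern.** A t-test on individual surveys treats each survey as a separate piece of information. Ratings from one person tend to resemble each other, so several surveys from one clinician carry less information than the same number from different clinicians. If the raters before and after training are different people, a difference between two small groups of raters can pass for a training effect. If they are the same people, a survey-level unpaired test ignores the pairing and wastes power.

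Team members' perception of and satisfaction with collaboration is a named secondary endpoint in section 2.2, and CSACD-N is its instrument. Section 6.3.2 plans significance statements from it for each discipline.

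**Working it through.** **Inputs from the documents.**
- Post-training meetings per discipline: 23 (protocol 3.1.5: "We estimate a total of 28 meetings will need to be recorded in order to obtain 23 meetings with each discipline").
- Trained clinicians: at least 20 (3.1.1), from six listed categories (3.4.2.1).
- Non-participating clinicians who may be observed: about 300 (3.3.2).
- Two-tailed alpha: 0.05 (6.3.2). The sentence refers to logistic regression, and no separate level is given for the t-tests.

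**Assumptions.** The documents give no ICC, no number of raters per discipline and no count of CSACD-N surveys before training. I take 23 surveys per discipline in each phase, spread evenly over *k* raters, and ICC from 0.05 to 0.5.

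**How much repetition is plausible.** Six categories × 23 meetings = 138 attendances by trained clinicians. Over 20 clinicians that is 138/20 = 6.9 each. Twenty is a floor, so the average falls if more are trained.

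**The plan's own figure.** With 23 against 23 independent surveys (44 degrees of freedom) the type I error is 0.0500. The nominal level is reproduced, but only under independence.

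**With clustering and no shared raters.** The design effect in a phase is DE = 1 + (23/*k* − 1) × ICC. The true standard error of the difference is √[(DE before + DE after)/2] times the one the t-test uses. The actual level is about 2 × [1 − Φ(1.96 / that ratio)].
- 23 raters before, 4 after, ICC 0.5: DE = 1 and 1 + 4.75 × 0.5 = 3.375. The mean is 2.19, the ratio 1.48 and the level about 0.19 (simulation 0.20).
- 4 raters in each phase, ICC 0.5: DE = 3.375 in both. The ratio is 1.84 and the level about 0.29 (simulation 0.31).

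**Simulated false-positive rates, nominal 5%.**

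| Raters before / after | Shared | ICC 0.05 | ICC 0.5 |
|---|---|---|---|
| 20 / 12 | none | 5% | 9% |
| 20 / 8 | none | 6% | 12% |
| 23 / 4 | none | 6% | 20% |
| 4 / 4 | none | 8% | 31% |
| 12 / 12 | half | 5% | 5% |
| 8 / 8 | half | 5% | 8% |
| 4 / 4 | all | 5% | 2% |

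In the last row, with ICC 0.5 and a true shift of 0.6 SD, the t-test has 59% power. A regression that includes clinician has 80%.

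The conservative result with shared raters assumes that clinicians do not differ in how much they change. If half the clinician variance is clinician-by-phase, the same 4 raters give 7.5%, 13% and 19% at ICC 0.1, 0.3 and 0.5.

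**Analysis on clinician means.** With the same raters in both phases, the paired t-test on clinician means gives 4.8-5.3%. With different raters, the unpaired test on means gives 4.9-5.2%. With half shared, the unpaired test on means is conservative (1.1-3.8% for ICC 0.1 to 0.5, 4 or 8 raters).

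**Which case applies.** Section 3.1.3 lists only non-participating clinicians before training, which points to little overlap. Section 4.3 says that the clinicians to be trained are also assessed beforehand, which points to more. The two have to be reconciled.

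**The case against.** The strongest reply is about size. The survey goes to everyone in the meeting, and about 300 non-participating clinicians may be observed, although repeat enrolment may inflate that number. If the raters before training are those clinicians, four of them per discipline is implausible. The six categories come from an eligibility list; the documents never define the disciplines for CSACD-N, and pooling physicians would raise the number of raters. This stands. A reader might take 31% as the expected error rate, but it is an extreme case.

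A reader might also infer that the p-values are wrong whatever the overlap. The table does not support that: with 12 raters per phase and half shared, the rate is about 5%.

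A third tempting inference is that speaking minutes by discipline, compared for clinicians who "speak in pre and post-CST meetings using linear regression and controlling for the length of the meetings", have the same fault. The documents do not show it. That outcome can be read as one discipline total per meeting, and splitting it by clinician would change the outcome.

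The t-test might be intended as paired, since 6.3.2 specifies paired tests for simulated meetings. That does not rescue it, because a survey-level paired test has no place for several surveys per clinician per phase.

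Finally, CSACD-N is one of many secondary endpoints in pilot work, the primary endpoint is qualitative, and no sample size rests on this test. That limits the importance of the point but does not make the test right.

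**Conclusion.** The point holds for CSACD-N. The stated test has no clinician term, the protocol itself says clinicians recur, and no other text corrects it, so the nominal 5% level is not in general held. The documents fix neither direction nor size. Under the assumptions above, the error rate runs from near nominal, with many raters or partial overlap, to clearly inflated when few raters supply one phase and overlap is small. It is too low when the same few people rate in both phases and change alike.

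Confidence is high that the test is mis-specified and low on how much it matters in this unit. The figures depend on 23 surveys per phase. The documents also give other meeting counts (at least 56 per discipline in 3.3.2; 230 before and 230 after in the SAP), and more surveys from the same raters would raise the design effect. The conclusion does not extend to the speaking-minutes regression or to the primary endpoint.

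**What to change.** In protocol 6.2 and 6.3.2, replace the CSACD-N t-tests with one linear mixed model for the total score. It should have fixed effects for phase, discipline and their interaction, random intercepts for clinician and for meeting, and Satterthwaite or Kenward-Roger degrees of freedom. Report each discipline's before/after contrast with its interval from that model. If there are too few raters for the model to fit, use one mean score per clinician per phase: paired where the same clinicians rate in both phases, unpaired where they differ. State that the unpaired version is conservative when some raters are shared. Leave the speaking-minutes analysis as it is.

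Reconcile 3.1.3 and 4.3 on who is assessed before training, and report the number of raters, surveys per rater and overlap between phases.

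Most of the cost is wording. One item may touch data collection: section 8.2 describes surveys linked to a participant number under the heading for intervention clinicians, and nothing says that a non-participating clinician keeps one ID across repeat enrolments. That should be confirmed or put in place. The statistical cost is wider intervals where few clinicians supply the surveys.
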